10.11. Appendix 11. ECOG Performance Status

Grade	Descriptions

CCI - This section contained Clinical Outcome Assessment data collection questionnaires or indices, which are protected by third party copyright laws and therefore have been excluded.
 	

1. [Oken](#), 1982.

10.12. Appendix 12: Guidelines for Management of Toxicity

The following dose modification criteria should provide guidance for, but not act as a replacement for sound clinical judgment. The investigator should use clinical judgment to determine which drug may be contributing to the toxicity necessitating dose adjustment, and make the appropriate change for that drug. Dose modifications should be made after discussion with the GSK medical monitor.

10.12.1. Management of Selected Toxicities

Table 14 Dose Adjustment/Stopping Safety Criteria

Toxicity	Dose Adjustment/ Stopping Criteria	Management Guidelines
Thrombocytopenia	Grade 1 & 2	Continue dosing at same dose level with weekly or more frequent monitoring as necessary
	Grade 3	
 Hold GSK3368715 until resolved to Grade ≤ 1 within ≤ 14 days Monitor complete blood count (CBC) at least twice a week Discuss with GSK Medical Monitor Re-start GSK3368715 at a reduced dose Discontinue GSK3368715 if not resolved to Grade ≤ 1 within ≤ 14 days
	Grade 4	
 Discontinue GSK3368715 Monitor CBC every 2-3 days.
Anemia	Grades 1 & 2	Continue dosing at same dose level with weekly or more frequent monitoring as necessary
	Grade 3	
 Hold GSK3368715 until resolved to Grade ≤ 1 within ≤ 14 days. Transfuse and treat as necessary. Monitor CBC at least twice a week. Discuss with GSK Medical Monitor. Re-start GSK3368715 at a reduced dose. Discontinue GSK3368715 if not resolved to Grade ≤ 1 within ≤ 14 days.
	Grade 4	
 Discontinue GSK3368715. Transfuse and treat as necessary. Monitor CBC every 2-3 days.
PR Interval	An increase in the PR Interval to >250 msec	
 This interval should be based on the average of the triplicate ECGs Discontinue GSK3368715 Contact the medical monitor Maintain proper electrolytes similar to recommendations for QTcF

Toxicity	Dose Adjustment/ Stopping Criteria	Management Guidelines
QRS Interval	An increase of >20% from baseline	
 This interval should be based on the average of the triplicate ECGs Discontinue GSK3368715 Contact the medical monitor Maintain proper electrolytes similar to recommendations for QTcF
QTcF	If >30msec and < 60 msec change from baseline AND manual QTcF <500 msec (average of three ECGs over at least 15 minutes)	
 Continue current dose of GSK3368715 
 Supplement electrolytes, particularly potassium and magnesium, to recommended levels: 
 Maintain serum potassium > 4 mol/L Maintain serum magnesium levels >0.85 mmol/L Discontinue any concomitant medications with potential for QTcF prolongation. Consider 24 hour or longer telemetry monitoring if clinically indicated.
	If ≥ 60 msec change from baseline occurs OR QTcF ≥ 500 msec (average of three ECGs over at least 15 minutes)	Discontinue GSK3368715 and notify the GSK Medical Monitor.
Liver		Refer to procedures outlined in Section 7.1.1 Liver Safety Required Actions and Follow up Assessments
Diarrhea	Grade 1	Initiate supportive care including loperamide.
	Grade 2	
 Initiate supportive care including loperamide. Consider hold of GSK3368715 Discuss with GSK Medical Monitor.
	Grade 3	
 Treat as above plus consider intravenous (IV) hydration, hospital admission and prophylactic antibiotics as appropriate. Hold GSK3368715 Discuss with GSK Medical Monitor. Re-start GSK3368715 at a reduced dose Discontinue GSK3368715 if not resolved to Grade ≤ 1 within ≤ 14 days
	Grade 4	
 Above plus consider intravenous (IV) hydration, hospital admission and prophylactic antibiotics as appropriate. Discontinue GSK3368715

Toxicity	Dose Adjustment/ Stopping Criteria	Management Guidelines
Nausea/Vomiting	Grade 1	
 Initiate supportive care with antiemetics as necessary.
	Grade 2	
 Initiate supportive care with antiemetics as necessary Consider hold of GSK3368715 until resolved to Grade \leq 1 within \leq 14 days Discuss with GSK medical monitor
	Grade 3	
 Supportive care as above, plus consider intravenous (IV) hydration, hospital admission and IV nutrition as appropriate. Hold GSK3368715 until resolved to Grade \leq 1 within \leq 14 days Discuss with GSK Medical Monitor. Re-start GSK3368715 at same dose if resolved within \leq 2 days Re-start GSK3368715 at reduced dose if resolved $>$ 2 days Discontinue GSK3368715 if not resolved to Grade \leq 1 within \leq 14 days
	Grade 4	
 Supportive care as above, plus consider intravenous (IV) hydration, hospital admission and IV nutrition as appropriate Discontinue GSK3368715 if lasting $>$2 days despite supportive care
All Other Toxicity*	Grade 1	
 Continue dosing with no change
	Grade 2	
 Continue dosing with no change 
OR
 
 Hold GSK3368715 for up to 1 week for toxicity to be $<$ Grade 2, then continue at the same dose (dose reduction is required if the grade 2 toxicity is considered a DLT)
	Grade 3	
 Hold GSK3368715 until resolved to Grade \leq 1 within \leq 14 days Discuss with GSK Medical Monitor Re-start GSK3368715 at a reduced dose 
Discontinue GSK3368715 if not resolved to Grade \leq 1 within \leq 14 days
 
Exception: In case of clinically insignificant laboratory abnormalities resolving \leq 2 days, re-start at same GSK3368715 dose possible after consultation of GSK Medical Monitor

	Grade 4	
 Discontinue GSK3368715 Restart of GSK3368715 may be considered upon

Toxicity	Dose Adjustment/ Stopping Criteria	Management Guidelines
		agreement between the GSK medical monitor and investigator in case of toxicities such as laboratory abnormalities (1) not associated with severe clinical symptoms requiring hospitalization, (2) lasting \leq 2 days, and (3) responding to supportive care
Venous Thromboembolism	Grade 2-4	
 • Medical care including Anticoagulation and follow-up according to standard of care • Discontinue GSK3368715 • Restart of GSK3368715 may be considered upon agreement between the GSK medical monitor and investigator in case the investigator believes there is benefit to the participant, participant is reconsented and the participant is appropriately anticoagulated. • In situations where full anticoagulation is not medically appropriate, discontinue GSK3368715

Note: Exceptions to \leq the drug-related Grade 1 requirement may be made for certain AEs as defined in Section 4.1.3.

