Nausea	
 • Grade 3 persisting >3 days despite BSC^a
Vomiting	
 • Grade 3 or 4 persisting > 3 days despite BSC^a
Diarrhea	
 • Grade 3 or 4 persisting > 3 days despite BSC^a
Fatigue	
 • Grade 3 persisting > 5 days
Hypertension	
 • Grade 3 that cannot be controlled with medical therapy • Grade 4
ECG-change	
 • > 20 msec extension of the QRS-interval compared to baseline
Laboratory abnormality	
 • Grade 3 persisting > 3 days despite BSC^a • Grade 4
Any other	
 • Grade 2 leading to frequent dose interruptions despite BSC^a and limiting GSK3368715 dosing to <80% of expected dose • Grade 2 requiring delay of GSK3368715 administration for > 14 days • Grade \geq3

DLT criteria for Hematologic Toxicity	
Neutropenia	
 Grade 3 persisting > 3 days despite BSC^a Febrile neutropenia Grade 4
Thrombocytopenia	
 Grade 3 persisting > 3 days despite BSC^a Grade 3 associated with clinically significant hemorrhage Grade 4
Any other ^b	
 Grade 2 and 3 leading to frequent dose interruptions despite BSC^a and limiting GSK3368715 dosing to < 80% of expected dose Grade 3 persisting > 3 days despite BSC^a Grade 4
Venous Thromboembolism	
 Grade 2 venous thromboembolism (VTE) that requires systemic anticoagulation or VTE Grade ≥ 3 during the first 8 (± 1) weeks or until study discontinuation (e.g., disease progression), whichever occurs sooner.

ALT=alanine aminotransferase; AST=aspartate aminotransferase; BSC=best supportive care; DLT=dose-limiting toxicity; ECG=electrocardiogram; ULN=upper limit of normal

- a. Best supportive care if available, according to institutional standards
b. With the exception of lymphocytopenia

For participants who experience a toxicity that meets the criteria of DLT, administration of GSK3368715 will be held pending management and resolution of the toxicity.

Participants who withdraw from the study before completing 21 days of intervention for reasons other than DLT may be replaced at the discretion of the sponsor.

Guidance for the management of toxicity, including dose modification algorithms, is provided in [Appendix 12](#).

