 - b) Any history of coronary artery disease, including acute coronary syndromes, myocardial infarction, unstable angina, and history of coronary angioplasty, or stenting
 - c) Presence of a cardiac pacemaker or implanted defibrillator.
 - d) AV-block (asymptomatic 2nd degree Type II or 3rd degree and any degree AV block if related to heart disease or if symptomatic), RBBB (right bundle branch block), LBBB (left bundle branch block), and any fascicular hemiblocks.
 - e) A QRS interval at Screening or Baseline ≥ 110 msec.
 - f) Patients with any symptomatic or sustained arrhythmias (past or present), including but not limited to:
 - Atrial fibrillation.
 - Atrial flutter
 - Ventricular tachycardia
 - Ventricular fibrillation
 - Supraventricular tachycardia
 - g) Current or past congestive heart failure.
 - h) Evidence of a left ventricular ejection fraction below the institutional lower limit of normal on Screening echocardiogram.
 - i) Evidence of significant structural heart disease on echocardiography at Screening (including any valvular disease greater than “mild” in severity)
 - j) Cardiac troponin > upper limit of the reference range at Screening.

Prior or Concomitant Anti-cancer Therapies

9. Treatment with any local or systemic anti-neoplastic therapy or investigational anti-cancer agent within 14 days or 4 half-lives, whichever is longer, up to a maximum wash-out period of 28 days prior to initiation of study drug administration

EXCEPTION NOTE: Anti-androgen therapies for prostate cancer, such as bicalutamide, must be stopped 28 days prior to first dose of GSK3368715. Second-line hormone therapies such as enzalutamide or abiraterone should be stopped 14 days prior to enrolment. Participants with prostate cancer may remain on (i) luteinizing hormone-releasing hormone (LHRH) agonists or antagonists and/or (ii) low-dose prednisone or prednisolone (up to 10 mg/day).

Nitrosureas and mitomycin C must be stopped within 42 days prior to first dose of GSK3368715.

10. Allogeneic hematopoietic stem-cell transplantation
11. Toxicities from previous anti-cancer therapies have not resolved to baseline or NCI-Common terminology criteria for adverse events (CTCAE) v5 \leq Grade 1 (except fatigue and alopecia [permissible at any grade] and peripheral neuropathy [which must be \leq Grade 2]) at the time of starting study intervention.

Prior or Concomitant Therapies:

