6.2. Dose Modification

Safety management guidelines, including dose modification algorithms, are provided. Please note, in cases where the investigator is directed to permanently discontinue study intervention, these instructions are mandatory as described in Section 7.

An overview of the available dose modification guidelines is presented in [Appendix 12](#).

All AEs are to be graded according to NCI-CTCAE, version 5. All dose modifications and the reason(s) for the dose modification must be documented in the eCRF.

Investigators should refer to the IB for GSK3368715 [GlaxoSmithKline Document Number [2017N334333_02](#)] and for additional information regarding the background of the drug and the management of other AEs or potential safety-related issues.

In case a dose modification is necessary, the dose level of one or both study interventions may be changed as determined by the investigator and sponsor/medical monitor.

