7.1.3. QRS Interval Stopping Criterion

An increase in the QRS interval of > 20 ms from baseline.

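### The QRS stopping criterion is an increase above 20 ms in Section 7.1.3 but above 20% in Table 14, and nothing says which prevails

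*Protocol*

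**What the plan says.** Three current places in the protocol set a limit on QRS change.

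- **Section 7.1.3 (stopping criterion):** "An increase in the QRS interval of > 20 ms from baseline". This is the whole section. It does not say whether a single tracing or a mean is meant.
- **Table 14, Section 10.12.1 (dose adjustment and stopping):** "An increase of >20% from baseline". The action is to stop the drug and contact the medical monitor, and the row offers no restart. On measurement it says: "This interval should be based on the average of the triplicate ECGs".
- **Table 6, Section 4.1.3 (DLT criteria):** "> 20 msec extension of the QRS-interval compared to baseline". The text below the table says that dosing is held after a DLT until the toxicity has been managed and has resolved.

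Section 7.1 lists, as separate grounds for permanent discontinuation, the QRS criterion of Section 7.1.3 and the dose modification criteria reached through Section 6.2. Section 6.2 points to Appendix 12 and adds that "in cases where the investigator is directed to permanently discontinue study intervention, these instructions are mandatory as described in Section 7". Appendix 12 opens in a softer tone: "The following dose modification criteria should provide guidance for, but not act as a replacement for sound clinical judgment".

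Exclusion criterion 8(e) bounds the baseline from above, since it excludes "A QRS interval at Screening or Baseline ≥ 110 msec".

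**The concern.** A stopping criterion should give the same answer wherever the site looks it up. Here one is an absolute change and the other a relative change, so they give different answers for any baseline other than 100 ms. An investigator working from the toxicity table and one working from Section 7 could act differently on the same ECG.

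QRS prolongation is, with PR prolongation, the cardiovascular risk named in Section 2.3.1 from the rat and dog studies. What is at stake is whether a participant stays on treatment and how the reason for stopping is to be read afterwards. There is also a smaller, indirect consequence for the DLT data. Section 7.4 counts a participant who stops before Day 21 for drug-related toxicity as DLT-evaluable. Such a participant could stop under Table 14 for a QRS change that does not reach the Table 6 QRS limit.

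**Working it through.** The plan states no figure to reproduce. The check compares the two thresholds directly.

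**Inputs**
- Absolute rule: increase above 20 ms (Section 7.1.3; the same limit appears in the Table 6 QRS row).
- Relative rule: increase above 20% (Table 14).
- Eligible baseline: below 110 ms (exclusion 8(e)).
- Baseline values in the table below: assumptions, because the documents give no lower limit or distribution.

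**Formulas**, with B the baseline QRS in ms
- The absolute rule triggers when QRS > B + 20.
- The relative rule triggers when QRS > 1.2 × B.
- Gap = (B + 20) − 1.2 × B = 20 − 0.2 × B. A positive gap means that the relative rule triggers earlier.
- Gap = 0 only at B = 20 / 0.2 = 100 ms.

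| Assumed baseline (ms) | Section 7.1.3 triggers above | Table 14 triggers above | Gap (ms) | Which triggers first |
|---|---|---|---|---|
| 75 | 95 | 90 | 5 | Table 14 |
| 80 | 100 | 96 | 4 | Table 14 |
| 90 | 110 | 108 | 2 | Table 14 |
| 100 | 120 | 120 | 0 | same |
| 105 | 125 | 126 | −1 | Section 7.1.3 |
| 109 | 129 | 130.8 | −1.8 | Section 7.1.3 |

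As B approaches 110 the gap approaches 20 − 22 = −2 ms.

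**Two examples, one in each direction**
- 80 to 98 ms: +18 ms, and 18/80 = +22.5%. Table 14 is met; Section 7.1.3 is not. The Table 6 QRS row is not met either.
- 108 to 129 ms: +21 ms, and 21/108 = +19.4%. Section 7.1.3 is met; Table 14 is not. The change also exceeds the Table 6 QRS limit.

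**Measurement basis.** Table 14 requires the triplicate mean and Section 7.1.3 is silent. SAP Section 5.3 averages triplicates for the ECG baseline, but that is an analysis convention and does not govern a site's decision to stop treatment.

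**Precedence.** Section 6.2 makes directed permanent discontinuation mandatory, Appendix 12 calls itself guidance, and Section 7.1 lists both routes side by side. None of these texts says which QRS limit prevails.

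**The case against.** The strongest reply has four parts.

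1. **The texts are not of equal rank.** Appendix 12 describes itself as guidance, applied after discussion with the medical monitor, while Section 7 treats meeting cardiac stopping criteria as ending treatment. This stands in part. It makes the conflict less stark, but the Table 14 row still directs a stop without qualification, and Section 6.2 gives such directions mandatory force.
2. **A site can comply with both.** Because Section 7.1 lists separate grounds, a site applying both would stop at whichever limit is reached first. This also stands, as far as it goes. The protocol does not say to do so, however, and neither rule is the more cautious across the eligible range. A site that reads only one place can therefore miss a stop in either direction.
3. **The clinical signal is weak so far.** Section 2.2.1.4.3 reports over 400 time-matched points with a concentration-QRS slope near zero and no systematic dose-dependent increase at 50 to 200 mg. That lowers the likely number of cases. It does not reconcile the criteria, which the protocol retains.
4. **Enrolment has ended** (SAP Section 2.1), so a correction has limited prospective use. That is fair, although the documents do not say whether anyone remains on treatment, and discontinuations and DLTs are still to be summarised and listed.

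A reader might go further and infer that DLT status, and so entry into the N-CRM, depends on which page the site consults. The documents do not support that. Table 6 alone defines the QRS DLT, in milliseconds; Table 14 defines no DLT, and Section 7.1.3 uses the same number as Table 6. Nor is Table 6 a third stopping rule, since it leads to a hold. A reader might also expect the SAP to use the same limit. The QRS limits in SAP Section 14.8.1 (below 75 and above 110 ms) are absolute reporting flags and need not match a change-from-baseline stopping rule.

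**Conclusion.** The inconsistency is real and lies between Section 7.1.3 and Table 14: two current QRS stopping criteria in different units, only one of them with a stated measurement basis, and no rule of precedence. It should be corrected because it bears on participant safety and is cheap to resolve.

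Its size is modest. For assumed baselines from 75 ms to just below 110 ms, the two limits differ by 0 to 5 ms, with the direction reversing at 100 ms. A wider gap can be obtained by assuming a lower baseline (20 − 0.2 × 70 = 6 ms at 70 ms), but nothing in the documents gives that value. With no baseline distribution, the number of participants affected cannot be computed.

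The effect on the DLT data is indirect only: for baselines below 100 ms, Table 14 can stop a participant for a change that is not a DLT under the Table 6 QRS row. Which criterion is clinically right is not a question that this review answers.

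**What to change.** Reconcile Section 7.1.3 and Table 14 to a single QRS stopping criterion with a single measurement basis, and check the result against the QRS row of Table 6 so that the relation between a DLT hold and a stop is deliberate. The sponsor decides which criterion and which basis apply.

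Because enrolment has ended, also state in the clinical study report which criterion was applied to any QRS-related discontinuation, so that the planned summaries and listings of discontinuations and DLTs can be interpreted.

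The cost is a short protocol clarification and a sentence or footnote in the report. No sample size, model or data collection changes.

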10.13. Appendix 13: Khorana Score

Table 15 Predictive model for chemotherapy-associated VTE in the ambulatory setting

Patient characteristic	Points
CCI - This section contained Clinical Outcome Assessment data collection questionnaires or indices, which are protected by third party copyright laws and therefore have been excluded.	

VTE: venous thromboembolism

Source: [Key](#), 2019

10.14. Appendix 14: Protocol Amendment History

The Protocol Amendment Summary of Changes Table for the current amendment is located directly before the Table of Contents (TOC).

This amendment applies to all sites participating in the conduct of the study.

Amendment 02 22-FEBRUARY-2019

This amendment applies to all sites participating in the conduct of the study.

Overall Rationale for the Amendment:

Protocol Amendment 2 includes the following:

- Changes and clarifications made in the Schedule of Activities Tables (Table 1- Table 3). The SoA Tables have been modified to reflect that the first 21 days is the DLT Period. Revisions have also been made in the timings and frequency of some assessments. Visit windows have been added.
- Update to CTCAE version 5.
- Minor change to Inclusion criteria by not allowing participants with potential liver metastases (ALT < 5 x ULN) from Part 1 (Dose Escalation)
- Minor change to Exclusion Criteria by allowing 1st degree AV block and 2nd degree type 1 AV block.
- Addition of higher dose strength capsules (250mg).
- Administrative changes made throughout the document

Section # and Name	Description of Change	Brief Rationale
1.1 Synopsis	Intervention Groups and Duration – Change First Cycle to DLT period	Cycle is considered to be study drug dispensation which is 28 days. DLT period is first 21 days and is now defined as this per the Schedule of Activities Table.
1.3 Schedule of Activities: Table 1 Screening Procedures	Added Troponin I or T Include further details to Tumor	Troponin levels > upper limit are exclusionary as per criteria 8j. This testing was not originally included in the Screening Procedures table. Also added testing to Appendix 2 (Table 8). There is a requirement for tumor samples at screening for those in

Section # and Name	Description of Change	Brief Rationale
	biopsy requirements	PK/PD cohort compared to other cohorts
1.3 Schedule of Activities: Table 2 and 3 Schedule of Activities	
Significant changes made in the Schedule of Activities tables.
 
 • First 21 days changed from First Cycle to DLT period • Day 21 visit changed to Day 22 • Updated collection details for SAEs, AESIs and AEs • Moved Q3W assessments for ECOG and Vital Signs to Q4W • Added Urinalysis and Coagulations to Clinical Chemistry assessments • Modified timepoints for Tumor Imaging • Clarified Telephone Interview is only in Part 2 • Clarified language that the Tumor biopsy is optional unless patient is in PK/PD cohort and increased window for optional biopsy • Clarified language for extended 48 and 72 hour PK timepoints for Day 1 • Add a Day 22 sample for Circulating free (cf) ADMA and SDMA • Replaced Day 2 Whole Blood sample for PD 	
 • First 21 days is DLT period, this is not considered first cycle (Section 1.1 Synopsis) • Visit to occur after DLT period is completed • To align with Section 8.3.1 • To align with PK visit days every 4 weeks • As per Appendix 2 (Table 8), not initially included in Schedule of Activities Table • Reduce imaging requirements after first 8 months on treatment • As described in Section 8.10, not initially added to Schedule of Activities Table • To add clarity for biopsy requirements per cohort • To add clarity • Recent preclinical data suggests that greater reduction of cfADMA may be observed upon longer periods of treatment with GSK3368715 • Recent preclinical data suggest that no significant changes in the levels of intracellular ADMA-hnRNP-A1 would be expected on Day 2. Analysis of

Section # and Name	Description of Change	Brief Rationale
	
biomarkers with a Day 22 sample
 
 Add visit windows 	
PBMCs from Day 22 will increase the likelihood of observing greater changes for this biomarker.
 
 To add clarity
4.1.1 Part 1: Dose Escalation Phase	
Dose Escalation:
 
Move language here for dose increments after a grade 2 drug-related toxicity from statistics Section (9.2.1)
	Dosing increments should be found within Study Design Section 4
4.1.3 Dose-Limiting Toxicity, 5.2 Exclusion Criteria 11, 6.2 Dose Modification, 8.3 Adverse Events and Serious Adverse Events, 9.6.2.2 Adverse Events, 9.6.2.3 Clinical Laboratory Evaluations	Update CTCAE to version 5	New version released
5.1 Inclusion Criteria	
Criteria 2 Type of Participant and Disease Characteristics - Moved tumor biopsy details here and removed criteria 6
 
Criteria 3 Adequate organ function – allow ALT <5x ULN only in Part 2
	To add clarity
5.2 Exclusion Criteria	
Criteria 8d – Remove 1st degree AV block exclusion, clarify 2nd and 3rd degree
 
Criteria 12 – Moved to Section 6.7.1
	
AV block grade 1 and AV block grade 2 Type 1 (Wenckebach) are frequently observed in normal young healthy volunteers (Am J Cardiol. 1977 Mar;39(3):390-5.) and should not preclude participation in the absence of heart disease and in the absence of symptoms.

5.3.1 Meals and	Clarified that Day 8 is serial PK	Day 8 was omitted initially as a serial

Section # and Name	Description of Change	Brief Rationale
Dietary Restrictions	day.	PK day with requirements for fasting
Table 5 Study Intervention	Added 250mg dose strength	New dose strength added for higher dosing cohorts
6.7.1 Prohibited Medications	Moved radiotherapy here, added allowance for palliative radiotherapy and added Therapy to section title	To add clarity
6.7.1 Prohibited Medications, 8.5 Intervention of Overdose, 9.6.3.1 Pharmacokinetic Parameters, 9.6.3.2 Statistical analysis of Pharmacokinetic data, 10.5 Appendix 5: Genetics	Removed GSK3326595 reference	GSK3326595 is not included in this protocol
7.1 Discontinuation of Study Intervention	Clarified survival follow-up timeframe	To add clarity on participant level
7.1.5 Stopping Rules for Clinical Deterioration	Copied language here for participants receiving clinical benefit but with disease progression from Summary section	To add clarity
7.4 Participant and Study Completion	Clarify definitions for study completion for Part 1 and Part 2	To provide clarity
8.0 Study Assessments and Procedures	The reference to study procedures and their timing changed from Section 1.3 to Table 1-Table 3.	To provide clarity
8.1 Efficacy	Update tumor imaging timepoints to align with updated Schedule of Activities Table	Reduce scan frequency after 8 months.

Section # and Name	Description of Change	Brief Rationale
8.2.4 Holter Monitoring	Clarified screening Holter vs on treatment Holter	To provide clarity
8.7.3 Tumor Biopsy Collection/Surgical Procedures	Clarified tumor biopsy requirements per cohorts to align with updates made to Schedule of Activities Table	To provide clarity
8.10.1 Qualitative Telephone Interviews	Clarified that interviews will only be conducted in Part 2	Align with Schedule of Activities Table
9.4.2.1 Efficacy Analyses	Clarify futility timeframe	To provide clarity
Whole Document	Administrative corrections were made throughout the protocol to correct minor inconsistencies and typographical errors	Provide clarity and correction.

Amendment 01 12-JULY-2018

This amendment applies to all sites participating in the conduct of the study.

Overall Rationale for the Amendment:

All revisions made were as per requirements from FDA.

Section # and Name	Description of Change	Brief Rationale
Section 4.1.3 Dose-Limiting Toxicity – Table 4	Modified DLT definitions to include 1) non-hematologic toxicities of Grade ≥ 3 regardless of duration except those as indicated in Table 4 and Grade 2 which lead to frequent dose interruptions despite best standard of care and limit dosing of GSK3368715 to <80% of expected dose or a delay of dosing >14 days 2) Grade 3 thrombocytopenia with significant haemorrhage or other hematologic toxicities leading to	Address required changes per FDA.

Section # and Name	Description of Change	Brief Rationale
	frequent dose interruptions despite best standard of care and limit dosing of GSK3368715 to <80% of expected dose	
Section 5.1 Inclusion Criteria, Number 2	Inclusion criteria for transitional cell carcinoma of the Urothelium updated to require participants to have progressed at least one line of systemic therapy.	Address required changes per FDA.
Section 10.12.1 Management of Selected Toxicities – Table 11	
Incorporate
 
1) a hold of study drug, GSK3368715, for most related Grade 3 adverse events with possible re-start at reduced dose level for thrombocytopenia, anemia, diarrhea, nausea/vomiting, and all other non-hematologic toxicities as indicated in Table 11
 
2) discontinuation of study drug for related Grade 4 adverse events of any duration (excluding most lab abnormalities).
 
Edited incorrect compound number from GSK3326595 to GSK3368715.
	Address required changes per FDA.

